**Non-Interventional Study Protocol (PASS) with secondary use of data**

**REDACTED PROTOCOL**

LCZ696B2014

Title	Non-interventional post-authorization multi-database safety study to characterize the risk of angioedema and other specific safety events of interest in association with use of Entresto® (sacubitril/valsartan) in adult patients with heart failure
Protocol version identifier	v01.1 – first amendment
Date of last version of protocol	22-March-2022
EU PAS register number	EUPAS18214 ( http://www.encepp.eu/encepp/viewResource.htm?id=18809 )
Active substance	Sacubitril/valsartan (LCZ696) ATC code: C09DX04
Medicinal product	Entresto®
Product reference	EMA/H/C/004062
Procedure number	EMA/H/C/004062/MEA/002
Name of Marketing authorization holder(s)	Novartis Europharm Limited
Joint PASS	No

---

Research question and objectives      With this non-interventional study, real-world data will be gathered on the risk of angioedema and other potential or identified risks (as listed in the Entresto® Risk Management Plan) associated with LCZ696 as compared to ACE inhibitors in adult patients with heart failure

Country (-ies) of study      Denmark, Germany, Italy, the Netherlands, Spain, United Kingdom

Author      

---

## List of abbreviations

---

ACE(I)	Angiotensin Converting Enzyme (Inhibitor)
ADM	Administrative
AE	Adverse Event
ARB	Angiotensin Receptor Blocker
ARNI	Angiotensin Receptor Neprilysin Inhibitor
ARS	Agenzia Regionale di Sanità della Toscana
ATC	Anatomical Therapeutic Chemical
BIPS	Leibniz Institute for Prevention Research and Epidemiology – BIPS (formerly Bremer Institut für Präventionsforschung und Sozialmedizin)
BMI	Body Mass Index
BNF	British National Formulary
CHMP	Committee for Medicinal Products for Human Use
CI	Confidence Interval
CKD	Chronic Kidney Disease
COPD	Chronic Obstructive Pulmonary Disease
COVID-19	Corona Virus Disease – 2019
CPRD	Clinical Practice Research Datalink
CRO	Contract Research Organization
Db	Database
DE	Germany
DK	Denmark
EMA	European Medicines Agency
EMR	Electronic Medical Record
ENCePP	European Network of Centres for Pharmacoepidemiology and Pharmacovigilance
ES	Spain
EU	European Union
FNR	False negative rate
GePaRD	German Pharmacoepidemiological Research Database
GM	German Modification
GP	General Practitioner
GPP	Good Pharmacoepidemiology Practices
HES	Hospital Episode Statistics
HF	Heart Failure
HFrEF	Heart Failure with Reduced Ejection Fraction
HIV	Human Immunodeficiency Virus
HR	Hazard Ratio
HSD	Health Search Database
ICD-9	The International Classification of Diseases, 9 th Revision
ICD-10	The International Classification of Diseases, 10 th Revision
ICPC	International Classification of Primary Care
IQR	Interquartile Range
IR	Incidence Rate
IT	Italy

---

---

LBQ657	The active metabolite of the prodrug sacubitril
LCZ696	Sacubitril/valsartan
MRA	Mineralocorticoid Receptor Antagonist
NEP	Neutral Endopeptidase
NHS	National Health Service
NIS	Non-Interventional Study
NL	The Netherlands
NLP	Natural Language Processing
NSAID	Non-Steroid Anti-Inflammatory Drug
NYHA	New York Heart Classification
OTC	Over the Counter
PSOW	Propensity Score Overlap Weight
PARADIGM-HF	Prospective Comparison of ARNI with ACEI to Determine Impact on Global Mortality and Morbidity in Heart Failure
PASS	Post-Authorization Safety Study
PI	Principal Investigator
PPV	Positive predictive value
PRAC	Pharmacovigilance Risk Assessment Committee
PS	Propensity Score
PY	Patient-Year
R	R programming language
RAAS	Renin-Angiotensin-Aldosterone System
RCT	Randomized Controlled Trial
RMP	Risk Management Plan
RR	Relative Risk
SAP	Statistical Analysis Plan
SAS	Statistical Analysis Software package from SAS Institute Inc.
SD	Standard Deviation
SHI	Statutory Health Insurance
SIDIAP	Sistema d'Informació per al Desenvolupament de la Investigació en Atenció Primària
SMD	Standardized Mean Difference
SmPC	Summary of Product Characteristics
STROBE	Strengthening the Reporting of Observational Studies in Epidemiology
TIA	Transient Ischemic Attack
UK	United Kingdom
ULN	Upper Limit of Normal
UMLS	Unified Medical Language System
US	United States
WCIA	Werkgroep Coördinatie Informatisering en Automatisering
WHO	World Health Organization

---

[figure not shown]

---

## 2 Abstract

### Title

Non-interventional post-authorization multi-database safety study to characterize the risk of angioedema and other specific safety events of interest in association with use of Entresto® (sacubitril/valsartan) in adult patients with heart failure.

### Version and date

v01.1 (Update of Amendment 1) – 22-Mar-2022

### Name and affiliation of main author

### Rationale and background

LCZ696 (sacubitril/valsartan; ATC code C09DX04; Entresto®) exhibits a novel mechanism of action to treat heart failure (HF) with the angiotensin receptor neprilysin inhibitor (ARNI) by simultaneously inhibiting neprilysin (neutral endopeptidase; NEP) via LBQ657, the active metabolite of the prodrug sacubitril, and by blocking the angiotensin II type-1 (AT1) receptor via valsartan. It was approved in the European Union (EU) on 19 November 2015. In the EU, Entresto is indicated in adult patients for treatment of symptomatic chronic heart failure with reduced ejection fraction.

As agreed with the Committee for Medicinal Products for Human Use (CHMP), Novartis will conduct a non-imposed non-interventional Post-Authorization Safety Study (PASS; category 3) for the risk of angioedema in association with sacubitril/valsartan use. In addition to the risk of angioedema, this study will investigate the risks of hypotension, hyperkalemia, hepatotoxicity, and renal impairment (all included in the Risk Management Plan [RMP] for Entresto as 'important identified risks', except 'hepatotoxicity' which is listed as 'important potential risk').

### Research question and objectives

This non-interventional study aims to estimate the risk for angioedema associated with use of sacubitril/valsartan, as well as the risks for hypotension, hyperkalemia, hepatotoxicity, and renal impairment, compared to use of angiotensin converting enzyme inhibitors (ACEIs) in adult patients with HF.

The objectives of the study are:

#### Primary objective

1. To estimate the incidence of specific safety events of interest in HF patients newly starting treatment with sacubitril/valsartan (regardless of prior use of ACEIs or angiotensin II receptor blockers (ARBs))
2. To estimate the incidence of all specific safety events in HF patients newly starting treatment with sacubitril/valsartan without prior exposure to ACEIs or ARBs

The primary safety event of interest is:

- Angioedema

Secondary events of interest are:

- Hypotension
- Hyperkalemia
- Hepatotoxicity
- Renal impairment

---

**Secondary objectives:**

1. To estimate the incidence of angioedema, hypotension, hyperkalemia, hepatotoxicity, and renal impairment in adult HF patients newly starting treatment with ACEIs (patients without prior exposure to ACEIs/ARBs)
2. To estimate the incidence of angioedema, hypotension, hyperkalemia, hepatotoxicity, and renal impairment in adult HF patients with ACEI exposure (regardless of prior use of ACEIs/ARBs)

**Exploratory objectives:**

1. To estimate the relative risk of angioedema in adult HF patients newly starting treatment with sacubitril/valsartan (without prior ACEI/ARB exposure) as compared to adult HF patients newly starting treatment with ACEIs (without prior ACEI/ARB exposure)
2. To estimate the relative risk of angioedema in adult HF patients newly starting treatment with sacubitril/valsartan (regardless of prior ACEI/ARB exposure) versus adult HF patients newly starting treatment with ACEIs (without prior ACEI/ARB exposure)
3. To estimate the relative risk of angioedema in adult HF patients newly starting treatment with sacubitril/valsartan (regardless of prior ACEI/ARB exposure) vs. HF patients with ACEI exposure (regardless of prior ACEI/ARB exposure)

**Study design**

Cohort study to estimate the incidence and relative risks for angioedema, hypotension, hyperkalemia, hepatotoxicity, and renal impairment in adult patients diagnosed with HF (prevalent and incident) newly starting sacubitril/valsartan or using ACEIs.

**Population**

The overall study population will consist of adult patients ( $\geq 18$  years of age) with prevalent or incident HF initiating either sacubitril/valsartan or using an ACEI (no concomitant use of sacubitril/valsartan and ACEI) during the study period, identified from seven European electronic healthcare databases from 6 countries: Germany (DE), Denmark (DK), the Netherlands (NL), Italy (IT), Spain (ES), and the United Kingdom (UK). Stratifications will be made for prior use of ACEIs/ARBs.

For each database, the study period starts at the time Entresto® (sacubitril/valsartan) was launched in the country. The end of the study period will be June 2021 at the latest.

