**Variables**

The primary outcome of interest is angioedema. In addition, hypotension, hyperkalemia, hepatotoxicity, and renal impairment will be studied. These events will be identified, using the database specific coding systems, e.g., Read, International Classification of Diseases (ICD) 9th or 10th revision, Clinical Modification (ICD-9/-10 CM), ICD-10 German Modification (GM), or International Classification of Primary Care (ICPC), the latter supplemented with natural language processing.

The exposures of interest are new treatment with sacubitril/valsartan or an ACEI. Patients must have a recorded diagnosis of HF prior to or within three months (90 days) after the first prescription (or pharmacy fill) of sacubitril/valsartan or an ACEI. Any ACEIs used in the countries covered by the databases during the study time period will be included. Patients will be considered ACEI/ARB-naïve (incident, or new users) if they have not been prescribed an ACEI/ARB within the 365 days before the index date.

We will capture information on potential confounders such as patient demographics/characteristics, comorbidities, and concomitant medications at the index date or during a minimal 365-day look-back period before the index date.

---

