### 5.1.1 Angioedema risks associated with use of other neprilysin-inhibitors

Sacubitril is a neprilysin-inhibitor. Neprilysin (also known as ‘neutral endopeptidase’ [NEP]) increases levels of bradykinin, which is associated with angioedema and may have an important causal role. Studies with omapatrilat – an antihypertensive agent that has both NEP- and ACE-inhibiting properties – demonstrated that dual ACE- and neprilysin-inhibition increased the risk for serious angioedema ([Kostis et al 2004](#)) probably by inhibiting all three enzymes responsible for the breakdown of bradykinin (ACE, NEP, and aminopeptidase P) ([Fryer et al 2008](#)). Unlike omapatrilat, sacubitril’s active metabolite LBQ657 is a selective NEP-inhibitor and blocks only one of these three enzymes. The other active substance of sacubitril/valsartan, the ARB

valsartan is known to have a lower risk of angioedema compared to ACEIs (Fryer et al 2008, Toh et al 2012).

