#### 7.1.1 Rationale for study design

To obtain a robust estimate of the incidence of angioedema – the primary safety event of interest – as well as of the other safety events (i.e. hypotension, hyperkalemia, hepatotoxicity, and renal impairment) in patients newly starting sacubitril/valsartan (incident users), an initial cohort of all sacubitril/valsartan initiators will be identified (regardless of prior exposure to ACEIs or ARBs) with patient accrual beginning at the specific launch date of sacubitril/valsartan (see [Table 7-1](#)) in those EU countries from which healthcare database information will be used for this study (see [Section 7.4](#) ‘Data sources’). In addition, an initial contemporaneous comparator cohort of ACEIs initiators will be identified. Data collection will end when the necessary sample size of 24,000 PYs is reached (see [Section 7.5](#) ‘Study size/power calculation’), but on 31 December 2021 at the latest (even when the target sample size is not reached).

A new user design ([Ray 2003](#), [Food and Drug Administration 2013](#), [Yoshida et al 2015](#)) is proposed to minimize the risk of a prevalent user bias and depletion of susceptibles. This is of particular importance for ACEIs users. Sacubitril/valsartan was newly introduced to the market and the cohort of users therefore automatically consists of new users. As indicated in the sacubitril/valsartan ‘Summary of Product Characteristics’ (SmPC), it is contraindicated for patients with a known history of angioedema related to previous ACEI or ARB therapy, or with hereditary or idiopathic angioedema. The combination of sacubitril/valsartan with an ACEI is contraindicated due to the increased risk of angioedema. Sacubitril/valsartan must not be initiated within 36 hours after taking the last dose of ACEI therapy.

Since the majority of sacubitril/valsartan users are expected to have been treated with an ACEI or ARB before starting sacubitril/valsartan, these patients will likely have a lower baseline risk of angioedema as susceptible patients have been depleted. ACEI initiators who are treatment

naïve to ACEIs and ARBs however, will likely have a higher baseline risk of angioedema since this population includes all patients who are susceptible to an angioedema event.

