Accruing the required sample size for the comparison of patients initiating sacubitril/valsartan treatment without prior ACEI/ARB use with those newly initiating treatment with ACEIs/ARBs within the proposed timelines will be very unlikely. It should be expected that many HF patients (both prevalent and incident) will have been previously exposed to an ACEI used as treatment for hypertension or other comorbid diseases prevalent in HF patients (e.g., acute myocardial infarction, diabetic nephropathy). A US study in patients with incident HF diagnosed between 2005 and 2008 from four sites participating in the Cardiovascular Research Network (CVRN) found an exposure prevalence to ACEIs or ARBs in patients with incident HFrEF (n=3,941, mean age 69 years) of 43% ([Goldberg et al 2013](#)). In the European ‘ESC-HF Long-Term Registry’ a prospective cohort study with primary data collection, including over 7,400 patients with prevalent chronic HF (median age 66 years) were enrolled over two years. In the subgroup of patients with HFrEF (n=4,792), 92.2% were treated with ACEIs or ARBs at baseline ([Maggioni et al 2013](#)). Thus, indicating that the absolute number of ACEI initiators who are treatment naïve to ACEIs and ARBs will be limited. If necessary, it was initially planned to supplement the contemporaneous comparator cohort with a historical cohort of ACEI initiators who are treatment naïve to ACEIs using data prior to Entresto® market approval if needed. However, the most recent interim report for the LCZ696B2014 study identified a total of 116,041 ACEI initiators being treatment naïve to ACEIs/ARBs [REDACTED] when both ARS and GePaRD were included. Based on these results, inclusion of a historical cohort of ACEI initiators treatment naïve to ACEIs/ARBs does not seem necessary.

In addition, to explore the impact of depletion of susceptibles we will assess the rate of events in users of ACEIs with prior use of ACEIs/ARBs.

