#### 7.3.1.1 Sacubitril/valsartan user cohorts

- Sacubitril/valsartan initiators regardless of prior ACEI/ARB use (cohort 1)

This group includes all patients fulfilling the inclusion criteria ([Section 7.2.4](#)) and using sacubitril/valsartan during the study period – regardless of prior exposure to ACEIs or ARBs.

- Sacubitril/valsartan initiators treatment naïve to ACEIs/ARBs (cohort 2)

Cohort 2 is the subset of patients from cohort 1- who did not use ACEIs/ARBs in the 365 days prior to the index date.

---

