### 7.3.1.2 ACEI user cohorts

- ACEIs – users regardless of prior ACEI/ARB use (cohort 3)

[figure not shown]
This group includes all patients fulfilling the inclusion criteria ([Section 7.2.4](#)) and using ACEIs during the study period – regardless of prior exposure to ACEIs or ARBs. This cohort will be a mix of prevalent and incident ACEI users.

- ACEIs – without prior use of ACEI/ARB - treatment-naïve (cohort 4)

Cohort 4 is the subset of patients from cohort 3. It includes patients who did not use ACEIs/ARBs in the 365 days prior to index date. This sub-cohort corresponds to new ACEIs users - naïve to ACEIs/ARBs.

Note: Patients can be included in more than one cohort. Patients changing from ACEI to sacubitril/valsartan will be included in the corresponding ACEI cohort, as well as the sacubitril/valsartan cohort (only the first change will be considered). Patients changing from sacubitril/valsartan to an ACEI, however, will be censored. [Figure 7-2](#) illustrates cohort allocation and start of follow-up based on various exposure scenarios for sacubitril/valsartan and ACEI users.

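### The depletion-of-susceptibles reasoning and check treat prior ARB use as equal to prior ACEI use, which dilutes the apparent depletion

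*Protocol*

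**What the plan says.** The abstract (Population) announces that "Stratifications will be made for prior use of ACEIs/ARBs", and its Variables paragraph gives the rule: "Patients will be considered ACEI/ARB-naïve (incident, or new users) if they have not been prescribed an ACEI/ARB within the 365 days before the index date". Sections 7.3.1.1 and 7.3.1.2 build the cohorts on the same merged rule. Cohort 2 is the subset of sacubitril/valsartan starters "who did not use ACEIs/ARBs in the 365 days prior to the index date". Of cohort 4, the ACEI counterpart, the text says: "It includes patients who did not use ACEIs/ARBs in the 365 days prior to index date". Cohorts 1 and 3 take patients whatever their prior exposure.

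Section 7.1.1 expects most sacubitril/valsartan starters to have had an ACEI or an ARB, and concludes that "these patients will likely have a lower baseline risk of angioedema as susceptible patients have been depleted". Later in the same section it plans a check: "to explore the impact of depletion of susceptibles we will assess the rate of events in users of ACEIs with prior use of ACEIs/ARBs".

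Against this, section 5.1.1 states that "valsartan is known to have a lower risk of angioedema compared to ACEIs". The time-course argument in 7.1.1 speaks of ACEIs alone: risk peaks soon after an ACEI is started, and patients who react to an ACEI stop taking it.

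Section 7.7.1.2.2 adds a sensitivity analysis by length of prevalent ACEI exposure in a subset of cohort 3. Section 7.3.3 lists prior ACEI and prior ARB use as two separate baseline variables.

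**The concern.** Depletion means that a patient has already taken a drug that would have revealed the susceptibility and did not react. By the protocol's own account an ARB provokes angioedema less often than an ACEI, so time on an ARB alone is a weaker screen. The merged rule ignores this in two places.

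- **ACEI users.** A patient with only an ARB in the past year who now starts an ACEI is at the start of the early high-risk period. In the 7.1.1 check this patient is grouped with patients who have long tolerated an ACEI, so the rate in the prior-use group is raised.
- **Sacubitril/valsartan starters.** In cohort 1, starters coming from an ARB are never separated from starters coming from an ACEI. The depletion statement covers both alike.

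What is at stake is interpretation. Depletion is the protocol's main caveat when cohort 1 is compared with ACEI-naïve patients, and a diluted check would understate how strong it is. Adjustment for the two baseline variables cannot replace the split in the cohort 1 versus 4 comparison, because cohort 4 contains no prior users by definition.

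**Working it through.** **The plan's own figure.** Section 7.5 expects 132 events in 24,000 PY. 132/24,000 = 5.5 per 1,000 PY, with exact Poisson 95% CI 4.60-6.52, which reproduces the stated 4.6-6.5. This figure does not depend on how prior use is classified.

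**Inputs for the dilution**
- ACEI angioedema rate in the first 30 days: 9.7-11.3 per 1,000 PY (section 5.1.2).
- ACEI rate after 6-12 months: about 2.6 per 1,000 PY (section 5.1.2).
- ACEI rate averaged up to one year in the same study that supplies the 2.6: 4.38 per 1,000 PY (Table 7-9, Mini-Sentinel row).
- ARB-only share of prior users, s: not given in the protocol; assumed 20-50%.

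**Formula.** Let k be the ratio of the rate in patients not screened by an ACEI to the rate in ACEI-experienced patients. Suppose ARB-only patients carry the full unscreened rate. Then
- merged prior-use rate / ACEI-experienced rate = 1 + s(k - 1);
- naïve rate / merged rate = k / [1 + s(k - 1)], where the undiluted contrast is k.

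**Values of k.** Averaged over follow-up: 4.38/2.6 = 1.685. First 30 days only: 9.7/2.6 = 3.73 to 11.3/2.6 = 4.35.

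| s | Inflation, k = 1.685 | Naïve/merged, k = 1.685 | Inflation, k = 3.73-4.35 | Naïve/merged, k = 3.73-4.35 |
|---|---|---|---|---|
| 20% | 1.14 | 1.48 | 1.55-1.67 | 2.41-2.60 |
| 50% | 1.34 | 1.26 | 2.37-2.67 | 1.58-1.63 |

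With follow-up-averaged rates, a true contrast of about 1.7 would appear as about 1.3 to 1.5. In every cell it stays above 1.

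**Events available in cohort 1.** Section 5.1 reports an interim rate of 0.7 per 1,000 PY. Over 24,000 PY that gives 24 × 0.7 = 16.8 events. An ARB-only stratum holding 20-50% of the person-time would have 3.4 to 8.4, that is about 3-8. For scale, 5 events in 7,200 PY (30%) give an exact 95% CI of 0.2-1.6 per 1,000 PY, and 8 events in 12,000 PY (50%) give 0.3-1.3.

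**The case against.** **Little that is planned depends on the merge.** The primary quantity is the cohort 1 rate in all initiators, which is valid whatever their history. The comparison that the protocol calls optimal, cohort 2 versus 4, excludes both prior classes. Prior versus naïve is not one of the three exploratory contrasts, and all comparisons are labelled exploratory. This stands: a reader might infer that the primary rate or the cohort 2 versus 4 hazard ratio is biased, and neither is. What remains exposed is the stated depletion check and the reasoning behind it.

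**Cohort 3 is partly covered.** The sensitivity analysis in 7.7.1.2.2 is indexed to ACEI exposure, so ARB-only time should not count there. This stands in part. It covers a subset of cohort 3, says nothing of cohort 1, and leaves the 7.1.1 check as worded.

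**The large multiples are fragile.** A reader might take inflation of up to 2.7-fold as applying to the whole prior-use rate. It does not: it sets a 30-day ACEI peak against a late rate, attributes the entire fall to depletion, and assumes that ARB use screens out no one. Nor do the documents support transferring an ACEI time course to sacubitril/valsartan starters. Setting the pooled 2.9 of section 7.5 against 2.6 gives k = 1.12 and inflation of only 1.02-1.06, although that mixes sources.

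**ARB users are not unscreened.** Section 5.1.1 says lower risk, not none, and says it of valsartan, which is itself a component of the study drug. Section 7.2.4 excludes recorded prior angioedema from every cohort. This stands: the fault is treating the two classes as equal, and the text does not show that ARB use depletes nobody.

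**The SAP may already split the groups**, and 7.3.1 can be read as defining naïve status per class. The SAP is not at hand. The cohort rules, the depletion statement and the check are all in the protocol, however, and no cohort uses the per-class reading.

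**Conclusion.** The point holds as a limited one. Sections 5.1.1 and 7.1.1 do not fit together: depletion is argued from ACEI experience, then credited to ACEI and ARB use alike, and the planned check is built on the merged group. The effect is to raise the prior-use rate and shrink the apparent depletion.

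The size is illustrative, because the protocol gives neither an ARB-only share nor a post-ARB rate. With an assumed share of 20-50%, inflation is about 1.14-1.34-fold on follow-up-averaged ACEI rates. About 2.7-fold is an upper bound for the first 30 days only. Both figures assume no screening by ARBs and attribute the whole time trend to depletion, so the true dilution may be smaller.

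A reader might go further and infer that depletion could look absent when it is present. The calculation does not support that for the point contrast: it shrinks but stays above 1 throughout.

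**What to change.** - **Section 7.7.1.2.2:** report the angioedema incidence rate in cohorts 1 and 3 by three prior-exposure levels: any ACEI in the previous 365 days, ARB only, and neither. Use the two variables already listed in 7.3.3.
- **Section 7.1.1, depletion check:** base it on prior ACEI use versus neither, and show ARB only separately.
- **Section 7.1.1, depletion statement:** limit it to prior ACEI use, or say that the effect is expected to be weaker after an ARB.
- Leave cohorts 2 and 4 unchanged.

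The cost is one further stratification of planned tables, with no new data. Cohort 3 is large enough to carry it (section 7.1.2 counts almost 567,000 ACEI users with ARS and GePaRD included). In cohort 1 the ARB-only stratum would hold about 3-8 events at the interim rate, so it should be labelled descriptive. The 365-day window also means that patients who used an ACEI earlier than that may still fall under ARB only; the report should say so.
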